#### 9.4 PATIENT DEMOGRAPHICS AND BASELINE CHARACTERISTICS

Baseline demographic and clinical characteristics will be summarized as percentages for categorical variables and as mean, standard deviation, median, minimum and maximum for continuous measures. The analyses of baseline characteristics will be performed for the ITT population.

#### 9.5 MEDICAL HISTORY

Medical history will be captured at the Screening visit.

#### 9.6 EXTENT OF EXPOSURE

The dose (mg) of study drugs administered, the total number of doses of study drug, and the duration of treatment (number of study cycles) will be summarized with descriptive statistics. The number and percentage of patients whose dose is modified at any time will be summarized by each type of modification by cycle and overall. The proportion of patients completing each cycle of treatment will be summarized.

#### 9.7 EFFICACY ANALYSES

Each patient will be assigned to one of the following categories: 1) complete response, 2) partial response, 3) stable disease, 4) progressive disease, 5) early death from malignant disease, 6) early death from toxicity, 7) early death because of other cause, or 8) unknown (not assessable, insufficient data).

Many of the efficacy measures will be based on disease assessments. The best clinical response as well as disease progression will be determined by the treating investigator. Scans should be kept on file in cases where independent review or confirmation may be warranted. Definitive disease progression will be based on standard criteria (Hallek et al. 2018) occurring for any reason (e.g., increasing lymphadenopathy, organomegaly or bone marrow involvement; decreasing platelet count, hemoglobin, or neutrophil count; or worsening of disease-related symptoms) other than lymphocytosis.

During the study period, all patients will be evaluated for response by CT or MRI within 14 days prior to Cycle 4, Day 1 for Cycle 3 assessment, and within 14 days prior to Cycle 13, Day 1 for Cycle 12 assessment, and at any other time point to confirm progression. Patients who fail to achieve a partial or complete response to umbralisib at the Cycle 3 assessment will discontinue study treatment. At that time, patients- will be provided appropriate options to receive established frontline therapy. Patients who demonstrate a partial or complete response will be treated until disease progression, unacceptable toxicity, or the end of the study.

#### 9.8 MISSING VALUE HANDLING PROCEDURES

In general, other than for partial dates, missing data will not be imputed and will be treated as missing. The algorithms for imputation of partial dates may vary depending upon the parameter.

#### 9.9 STATISTICAL ANALYSES

## 9.9.1 PRIMARY EFFICACY VARIABLE - PFS

The two primary efficacy outcomes are overall response rate (ORR) and progression-free survival (PFS). Time to progression event "Survival" curve will be presented using Kaplan-Meier method. Median time to event and the 95% confidence interval of the median times will be presented, if estimable. Median time to event will be tested against the null hypothesis value using a one-sample (one-sided) log-rank test.

PFS is defined as the interval from Cycle 1, Day 1 to the earlier of the first documentation of definitive disease progression or death from any cause.

Overall Response Rate (ORR) will be determined according to the criteria of the International Workshop on Chronic Lymphocytic Leukemia (Hallek et al. 2018).

We will estimate Overall Response Rate (ORR), which is defined as percent of patients who achieve CR or PR. We will also estimate exact 95% confidence intervals for the response rates. These will be followed by additional logistic regression analyses model to adjust for demographic and baseline parameters.

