| Study Rationale             | The purpose of this study is to evaluate the efficacy, safety, pharmacokinetic properties, and pharmacodynamic properties of umbralisib in treatment naïve chronic lymphocytic leukemia (CLL) patients.
Umbralisib is a highly-specific and orally available phosphoinositide-3-kinase (PI3K) delta ( $\delta$ ) inhibitor with nanomolar inhibitory potency, and high selectivity over the alpha, beta, and gamma Class I isoforms of PI3K. Umbralisib has completed a Phase I dose escalation trial and has been administered safely at daily doses up through 1200 mg QD.
In the Phase I study, 90 subjects with relapsed and refractory hematologic malignancies were treated with umbralisib, including 24 with CLL. The most commonly reported AEs (all grades, all causality) were diarrhea, nausea, and fatigue, the majority of which were Gr1/2. The only Gr≥3 AE in >10% of patients was neutropenia (13%). In the modified intention-to-treat population, which included subjects who received at least 800 mg per day of the original formulation or any dose of the micronized formulation and had at least one response assessment, 17 (85%) of 20 subjects with relapsed or refractory CLL achieved an objective response, with ten (50%) achieving a partial response with lymphocytosis, and the remaining three (15%) achieving stable disease.
Due to the differentiated safety profile, once-daily dosing and clinical activity in CLL with u mbralisib, the primary aim of this study is to evaluate the overall response rate and progression-free survival of umbralisib, while better understanding the PK/PD profile of umbralisib. |

| with |
|------|
| isib |
|      |
|      |
|      |

|           | Patients must meet all of the following inclusion criteria to be eligible for  |
|-----------|--|
|           | participation in this study:   |
|           | 1) Have a diagnosis of B-cell CLL that has not been previously treated and now   |
|           | warrants treatment consistent with accepted iwCLL criteria (Hallek2018)  |
|           | for initiation of therapy. Any one of the following conditions constitute CLL  |
|           | that warrants treatment:   |
|           | a) Evidence of progressive marrow failure as manifested by the onset or  |
|           | worsening of anemia and/or thrombocytopenia, or  |
|           | b) Massive (i.e., lower edge of spleen $\geq$ 6 cm below the left costal margin),  |

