|              | 
 
a) Symptomatic, or history of documented congestive heart failure (NY Heart Association functional classification III-IV) - See Appendix B
 
b) Myocardial infarction within 6 months of enrollment
 
c) Concomitant use of medication known to cause QT prolongation or torsades de pointes should be used with caution and at investigator discretion.
 
d) Angina not well-controlled by medication
 
e) Poorly controlled or clinically significant atherosclerotic vascular disease including cerebrovascular accident (CVA), transient ischemic attack (TIA), symptomatic peripheral arterial disease, angioplasty, cardiac/vascular stenting within 6 months of enrollment.
 
12) Malignancy (including myelodysplastic syndromes) within 3 years of study enrollment except for basal, squamous cell carcinoma or melanoma in situ , carcinoma in situ of the cervix, superficial bladder cancer not treated with intravesical chemotherapy or BCG within 6 months, localized prostate cancer following curative treatment and with a normal PSA.
 
13) Women who are pregnant or lactating.
 
14) Subjects requiring immediate cytoreductive therapy.
 
 |
|--------------|---|
| Study Design | 
 
This study is designed as a Phase 2, single-center, single-arm trial to evaluate the efficacy and safety of umbralisib, in patients with CLL. The primary objective will be measured by overall response rate (ORR).
 
Enrollment
 
Following Screening, qualified patients will be enrolled and receive the following: 
 
Umbralisib 800 mg once daily within 30 minutes of a meal.
 
 
 
During the study period, all patients will be evaluated for response by CT or MRI within 14 days prior to Cycle 4, Day 1 for Cycle 3 assessment, and within 14 days prior to Cycle 12 assessment, and at any other time point to confirm progression. Patients who fail to achieve a partial or complete response to umbralisib at the Cycle 3 assessment will discontinue study treatment. At that time, patients- will be provided appropriate options to receive established frontline therapy. Patients who demonstrate a partial or complete response to the end of the study.
 
The primary efficacy variable will be ORR.
 
   |

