#### 2. TRIAL OBJECTIVES AND ENDPOINTS

#### 2.1 STUDY OBJECTIVES

#### PRIMARY OBJECTIVE

• To evaluate the overall response rate (CR + PR)

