#### **SECONDARY OBJECTIVES**

- To determine the progression free survival of umbralisib in patients with CLL
- To assess safety of umbralisib, tolerability and other efficacy outcomes
- To determine the pharmacokinetics and pharmacodynamics of umbralisib

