# 4. STUDY DESIGN

#### 4.1 OVERVIEW OF STUDY DESIGN

This study is designed as a Phase 2, single-center, single-arm trial to evaluate the ORR and PFS of umbralisib in treatment naïve CLL patients requiring therapy. Daily doses of oral umbralisib will be administered in the absence of disease progression, unacceptable toxicity, or withdrawal from treatment. Treatment cycles are 4 weeks, with the efficacy evaluations within 14 days prior to Cycle 4, Day 1 for Cycle 3 assessment, and within 14 days prior to Cycle 13, Day 1 for Cycle 12 assessment, and at any other time point to confirm progression. Patients who fail to achieve a partial or complete response to umbralisib at the Cycle 3 assessment will discontinue study treatment. At that time, patients- will be provided appropriate options to receive established frontline therapy. Patients who demonstrate a partial or complete response will be treated until disease progression, unacceptable toxicity, or the end of the study. Enrollment will be up to 35 patients.

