## 9 STATISTICAL CONSIDERATIONS

#### 9.1 SAMPLE SIZE

This is a phase 2 study designed to assess the overall response rate (CR + PR) and progressionfree survival (PFS) of Umbralisib in treatment naïve patients with CLL. The primary endpoint is the overall response rate (ORR) from the time of treatment. The study will plan to enroll up to 40 subjects, and assuming 10% attrition, the study will have approximately 35 subjects remaining for analysis. Any subjects who are screen failures are not considered enrolled and may be replaced to meet the accrual goal. Enrollment is expected to be completed in approximately 18 months with 24 months follow up. The ORR for the standard of care is about 60%. We expect that Umbralisib treatment could lead to 80% ORR. A Simon 2-stage minimax design that differentiates ORRs of 0.60 (null hypothesis) and 0.80 (alternative hypothesis) will be used to assess treatment efficacy, with the probabilities of a type I error (falsely accepting a non-promising therapy) and type II error (falsely rejecting a promising therapy) both set at 0.10. Twenty seven patients will be accrued in the first stage of the study. If 18 or fewer patients have a response, then the study will be terminated and declared negative. If 19 or more patients have a response, then an additional 8 patients will be accrued to the second stage. At the conclusion of the study, if 25 or more patients have a response out of a total of 35 patients enrolled, the regimen will be considered worthy of further investigation.

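### Section 9.9.1 makes PFS a primary outcome, against the sections that make ORR the only primary, and tests it against a null value stated nowhere

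*Combined protocol and SAP*

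**What the plan says.** Two places make PFS primary alongside ORR:

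- Section 9.9.1, headed as the primary efficacy variable PFS: "The two primary efficacy outcomes are overall response rate (ORR) and progression-free survival (PFS".
- Synopsis, study rationale: "the primary aim of this study is to evaluate the overall response rate and progression-free survival of umbralisib".

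Four places say otherwise:

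- Section 2.1, the only primary objective: "To evaluate the overall response rate (CR + PR").
- Section 2.1, under secondary objectives: "To determine the progression free survival of umbralisib in patients with CLL".
- Synopsis, study design: "The primary efficacy variable will be ORR".
- Section 9.1: "The primary endpoint is the overall response rate (ORR) from the time of treatment".

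Section 4.1 pairs the endpoints without ranking them ("single-arm trial to evaluate the ORR and PFS of umbralisib"), and the opening of section 9.1 does the same.

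On the PFS analysis, section 9.9.1 asks for a Kaplan-Meier curve and the median with its 95% confidence interval, and then a test: "Median time to event will be tested against the null hypothesis value using a one-sample (one-sided) log-rank test". Section 9.2 sets two-sided 0.05 as the default level where nothing else is stated. PFS runs from registration in the Efficacy Endpoints part of section 2, and from Cycle 1, Day 1 in section 9.9.1.

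**The concern.** The choice of primary endpoint decides which result the trial is reported on. Here a reader of section 2.1 and a reader of section 9.9.1 could each report a different primary result and both be following the document.

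The PFS test has a second problem. A one-sample log-rank test compares observed events with the number expected under a null survival curve. Without the null there is no expected number and no test statistic. In a single-arm trial whose progression calls are made by the treating investigator (section 9.7), a null chosen after PFS data have been seen could be placed to give either answer. If PFS really were co-primary, the plan would also need a rule for combining it with ORR, and none is given.

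**Working it through.** **1. The plan's own figure.** Inputs from section 9.1: ORR 0.60 against 0.80, both error rates 0.10; stop if 18 or fewer of 27 respond; success if 25 or more of 35 respond. With X1 ~ Bin(27, p) and X2 ~ Bin(8, p),

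P(success) = sum over x = 19 to 27 of P(X1 = x) · P(X2 ≥ 25 − x).

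| True ORR | P(stop at stage 1) | P(success) |
|---|---|---|
| 0.60 | 0.816 | 0.0965 |
| 0.80 | 0.074 | 0.900 |

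A full search at these inputs returns the same minimax design. The ORR rule is correct on its own terms and uses nearly all of the stated 0.10.

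**2. Search for the PFS inputs.** The only null value in the documents is the ORR of 0.60. The only PFS median for CLL is in section 1.2.2.1: 24.0 months (95% CI 7.4 to not reached), from a post-hoc analysis of 20 relapsed or refractory patients. It is not designated as a null, and this trial is in treatment-naive patients. The PFS test is one-sided with no level attached. Against the two-sided 0.05 default it could be read as one-sided 0.05 or one-sided 0.025.

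**3. How much the missing null matters.** Assumptions, not plan figures: 35 patients, exponential PFS, no dropout, observed median 24 months. The 24 months of follow-up in section 9.1 is read in two ways.

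Z = (O − E)/√E, with E = person-time × ln 2 / null median.

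*24 months for each patient.* O = 35 × (1 − 0.5) = 17.5. Person-time = 17.5 / (ln 2 / 24) = 605.9 months.

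| Null median (months) | E | Z | One-sided p |
|---|---|---|---|
| 12 | 35.0 | −2.96 | 0.0015 |
| 15 | 28.0 | −1.98 | 0.024 |
| 18 | 23.3 | −1.21 | 0.11 |
| 24 | 17.5 | 0 | 0.50 |

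The result flips where E − z√E = 17.5. At z = 1.645, E = 25.87 and the null median is 605.9 × 0.693 / 25.87 = 16.2 months. At z = 1.960, E = 27.84 and it is 15.1 months.

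*24 to 42 months (uniform accrual over 18 months, then 24 months).* O = 21.35 and person-time = 739.3 months. For the same four nulls, Z = −3.27, −2.19, −1.33, 0 and p = 0.0005, 0.014, 0.091, 0.50. The flip points are 16.8 and 15.8 months.

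*Sensitivity to the observed median* (24 months each, one-sided 0.05): the flip point is 5.5 months at an observed median of 7.4, 12.6 at 18, 16.2 at 24 and 22.9 at 36.

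**4. If PFS were co-primary and success on either outcome counted.** The plan does not state this rule; independence is also assumed. Overall type I error = 1 − (1 − 0.0965)(1 − a), where a is the one-sided PFS level.

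| a | Overall type I error |
|---|---|
| 0.025 | 0.119 |
| 0.05 | 0.142 |
| 0.10 | 0.187 |

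**The case against.** The strongest reply is that little depends on this. The only go/no-go rule is the two-stage rule on ORR, no consequence is attached to PFS, and the objectives, synopsis design and sample-size section agree with one another. The intended ranking can therefore be recovered, with section 9.9.1 and one rationale sentence as outliers. The curve, median and confidence interval in section 9.9.1 can all be produced without a null; only the test sentence fails. The p-values above rest on one assumed median from a different population and on complete follow-up, although section 6.5 makes follow-up after stopping treatment depend on the patient's agreement. Section 9.2 allows exceptions to its default, so a one-sided test does not contradict it. Section 4.1 does not rank the endpoints. The gap between the two PFS start dates is probably days, and about four weeks at most if registration falls within the 28-day screening window.

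Much of this stands. The ORR rule is untouched, the flip points move with the assumed median, the level is missing rather than contradictory, section 4.1 is not itself a conflict, and the start-date mismatch is small. It does not remove the core. Section 9.9.1 is the operative analysis section, its heading and first sentence make PFS primary, and the test it prescribes lacks the one input it needs.

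**Conclusion.** The concern holds, and the correction is needed before analysis. The plan contradicts itself on the primary endpoint, and the PFS test cannot be carried out as written.

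In the illustration, moving the null median from 12 to 24 months takes one-sided p from 0.0015 to 0.50. With an observed median of 24 months, the test succeeds only for nulls below about 15 to 17 months, depending on the level and the follow-up reading. Those limits belong to the assumed inputs and are not properties of the design. What does not depend on them is that an unstated number determines the result.

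The ORR decision rule and its error rates are unaffected. The inflation to between 0.119 and 0.187 would arise only under an either-outcome rule that the plan does not contain.

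**What to change.** - Retitle section 9.9.1 with ORR as the sole primary outcome, since it is the only endpoint with a sized decision rule, and remove PFS from its opening sentence.
- Align the primary-aim sentence in the synopsis rationale.
- Move PFS to a secondary-endpoint section. Delete the one-sample log-rank test and report the Kaplan-Meier curve, the median and landmark rates, each estimate with a 95% confidence interval. Only the landmark rates are new.
- Use one PFS start date in both definitions.
- If the sponsor wants to keep the test, label it secondary and fix a justified null median and a numeric one-sided level by amendment before any PFS data are examined.

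The cost is protocol and SAP wording. Sample size, visits and the ORR rule do not change. Under the main option the sponsor gives up a formal PFS claim, which the trial was never sized to support.

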#### Progression-free survival (PFS)

PFS is defined as the interval from registration to the earlier of the first documentation of definitive disease progression or death from any cause.

Definitive disease progression based on standard criteria (Hallek et al. 2018) and occurring for any reason (i.e., increasing lymphadenopathy, organomegaly or bone marrow involvement; decreasing platelet count, hemoglobin, or neutrophil count; or worsening of disease-related symptoms) other than lymphocytosis.

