## 3.1 INCLUSION CRITERIA

Patients must meet all of the following inclusion criteria to be eligible for participation in this study:

- 1) Have a diagnosis of B-cell CLL that has not been previously treated and now warrants treatment consistent with accepted iwCLL criteria (Hallek 2018) for initiation of therapy. Any one of the following conditions constitute CLL that warrants treatment:
  - a) Evidence of progressive marrow failure as manifested by the onset or worsening of anemia and/or thrombocytopenia, or
  - b) Massive (i.e., lower edge of spleen ≥ 6 cm below the left costal margin), progressive, or symptomatic splenomegaly, or
  - c) Massive (i.e., ≥ 10 cm in the longest diameter), progressive, or symptomatic lymphadenopathy, or
  - d) Progressive lymphocytosis in the absence of infection, with an increase in blood absolute lymphocyte count (ALC) >50% over a 2-month period or lymphocyte doubling time of <6 months (as long as initial ALC was  $\geq$  30,000/µL), or
  - e) Autoimmune anemia and/or thrombocytopenia that is poorly responsive to corticosteroids or other standard therapy, or
  - f) Symptomatic or functional extranodal involvement (e.g. skin, kidney, lung, or spine), or
  - g) Constitutional symptoms, defined as any one or more of the following diseaserelated symptoms or signs occurring in the absence of evidence of infection:
    - i) Unintentional weight loss of  $\geq 10\%$  within the previous 6 months, or
    - ii) Significant fatigue (≥ Grade 2), or
    - iii) Fevers >100.5°F or 38.0°C for  $\ge$ 2 weeks, or
    - iv) Night sweats for >1 month.
- 2) Adequate organ system function, defined as follows:
  - a) Absolute neutrophil count (ANC)  $\geq$  1,000/mm^3 platelet count  $\geq$  30,000/mm^3, (ANC  $\geq$  500/mm^3 and platelet count  $\geq$  20,000/mm^3 permitted if known marrow involvement). Growth factors are permitted at any time during the study, but not to meet eligibility criteria.
  - b) Total bilirubin ≤1.5 times the upper limit of normal (ULN) (unless diagnosed with Gilbert's syndrome).
  - c) Alanine aminotransferase (ALT) and aspartate aminotransferase (AST) ≤2.5 x ULN if no liver involvement or ≤5 x the ULN if known liver involvement
  - d) Calculated creatinine clearance >30 mL/min (as calculated by the Cockcroft-Gault or MDRD formula, 24 hour urine Cr clearance also acceptable)
- 3) ECOG performance status  $\leq 2$
- 4) Male or female  $\geq$  18 years of age

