#### 4.4 DISCONTINUATION FROM STUDY TREATMENT

Patients will be discontinued from study treatment for any of the following reasons:

- Disease progression
- Failure to achieve a partial or complete response to umbralisib at the Cycle 3 assessment
- Intolerable toxicity related to study drug
- Patient requests to withdraw consent or discontinue treatment
- Pregnancy
- Inability of the patient to comply with study requirements
- Conditions requiring therapeutic intervention not permitted by the protocol
- Non-compliance/lost to follow-up
- Investigator discretion
- Discontinuation of the study

Patients who discontinue from study treatment prior to Cycle 12 (for reasons other than progressive disease) should continue to be followed for progression approximately every 3 months up until the time Cycle 12 would have occurred, then approximately every 6 months.

Patients who discontinue from study treatment after Cycle 12 for reasons other than disease progression should be followed for progression approximately every 6 months.

After withdrawal from protocol treatment, patients should be followed for AEs for 30 calendar days after their last dose of study drug. All new AEs occurring during this period must be reported and followed until resolution, unless, in the opinion of the investigator, these values are not likely to improve because of the underlying disease. In this case the investigators must record his or her reasoning for this decision in the patient's medical records.

All patients who have CTCAE Grade 3 or 4 laboratory abnormalities at the time of withdrawal should be followed until the laboratory values have returned to Grade 1 or 2, unless in the opinion of the investigator, it is not likely that these values are to improve because of the underlying disease. In this case, the investigator must record his or her reasoning for making this decision in the patient's medical records.

All patients that begin therapy outside of the scope of this protocol within 30 days of discontinuing umbralisib do not need to be followed for AEs, unless umbralisib is determined to be the direct cause of the AE in the opinion of the treating investigator. After 30 days from discontinuation of umbralisib, these AEs no longer need to be followed.

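### PFS as written runs on through frontline therapy after the mandatory Cycle 3 stop, and no rule covers new anti-CLL therapy for PFS, DOR or best overall response

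*Combined protocol and SAP*

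**What the plan says.** - **Objective.** Section 2.1, secondary objectives: "To determine the progression free survival of umbralisib in patients with CLL". Section 9.9.1 nevertheless names PFS beside ORR as a primary outcome and plans a one-sample log-rank test of it. The decision rule in 9.1 uses ORR only.
- **Definition.** Section 9.9.1: "PFS is defined as the interval from Cycle 1, Day 1 to the earlier of the first documentation of definitive disease progression". The only other event is death, whatever its cause. The efficacy endpoints section (2.2 in the contents list, printed as 1.3 in the body) has a different start: "PFS is defined as the interval from registration to the earlier of the first documentation of definitive disease progression or death from any cause".
- **Mandatory stop.** Section 9.7, and the same rule elsewhere: "Patients who fail to achieve a partial or complete response to umbralisib at the Cycle 3 assessment will discontinue study treatment". Section 4.1 adds: "At that time, patients- will be provided appropriate options to receive established frontline therapy".
- **Follow-up after a stop.** Section 4.4: "Patients who discontinue from study treatment prior to Cycle 12 (for reasons other than progressive disease) should continue to be followed for progression". It lists failure to respond at Cycle 3 among the reasons for stopping. Sections 6.3, 6.5 and 8 also keep patients who have not progressed under follow-up. None makes an exception once other therapy starts.
- **Best overall response.** Section 8.4 takes the best result between start of treatment and progression, with no cut-off at new therapy.
- **Outside therapy.** The one rule that mentions it, in 4.4, limits adverse event follow-up. Section 9.8 says only that missing data other than partial dates are not imputed.

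**The concern.** The switch is built into the design. Every patient enters with CLL that "has not been previously treated and now warrants treatment consistent with accepted iwCLL criteria", so some uptake of frontline therapy after a failed Cycle 3 assessment is likely, although the documents give no figure. A patient with stable disease at Cycle 3 leaves umbralisib at about 2.8 months while the PFS clock runs on under another treatment. If that treatment delays progression, the added time is credited to umbralisib.

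The same silence reaches two other endpoints. Read literally, best overall response could include a response reached on frontline therapy. DOR is affected only when a responder stops without progression and then starts something else.

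Two wording conflicts touch the same analysis: the PFS start date, and the follow-up schedule. For patients who stop before Cycle 12, 4.4 moves to 6-monthly checks once Cycle 12 would have been reached, while 6.5 keeps 3-monthly checks. For patients still on drug, 6.5 treats testing after Cycle 12 as outside the study, while the schedule table has an every-3-cycles column with no stated end.

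**Working it through.** **1. The plan's own figure.** The only sample-size calculation is for ORR (9.1): 27 patients, continue with 19 or more responses; 35 patients, success with 25 or more. With X1 ~ Bin(27, p) and X2 ~ Bin(8, p), P(success) is the sum over x = 19 to 27 of P(X1 = x) × P(X2 ≥ 25 − x).

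- p = 0.60: success 0.0965 (type I error), early stop 0.816.
- p = 0.80: success 0.900 (power), early stop 0.074.

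The stated design reproduces. There is no PFS figure to reproduce.

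**2. Who is affected.** Non-responders: 35 × 0.20 = 7 at the design ORR; 35 × 0.40 = 14 at the null ORR. Those in progression at Cycle 3 already have their event. The rest are affected if they switch.

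**3. Illustration.** Inputs:

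- Cycle 3 ends at 3 × 28 = 84 days = 2.76 months (Section 4.1).
- Responder median 24 months after Cycle 3. This is borrowed from Section 1.2.2.1, where it is the PFS median of all 20 relapsed or refractory CLL subjects, not of responders.
- Assumed, not in the documents: exponential times; untreated non-responder median mU = 6 or 12; frontline median mF = 24 or 48; share of non-responders in progression at Cycle 3, d = 0, 0.25 or 0.50; uptake among the others, u = 0.10, 0.25 or 0.50, with the switch at Cycle 3.

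With q the non-response rate and t months after Cycle 3:

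- As written: S(t) = (1 − q)·2^(−t/24) + q(1 − d)·[(1 − u)·2^(−t/mU) + u·2^(−t/mF)]
- Umbralisib only: the same with u = 0.

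The median is 2.76 + t where S(t) = 0.5.

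*Worked case* (q = 0.20, d = 0, mU = 6, mF = 48, u = 0.50):

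- As written, t = 22.31: 0.4200 + 0.0076 + 0.0725 = 0.500, median 25.07.
- Umbralisib only, t = 18.04: 0.4751 + 0.0249 = 0.500, median 20.80.
- Overstatement 25.07 − 20.80 = 4.27 months.

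*Whole grid at q = 0.20:*

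| Uptake | Smallest (d = 0.50, mU = 12, mF = 24) | Largest (d = 0, mU = 6, mF = 48) |
|---|---|---|
| 10% | 21.63 − 21.47 = 0.16 | 21.60 − 20.80 = 0.80 |
| 25% | 21.87 − 21.47 = 0.40 | 22.85 − 20.80 = 2.05 |
| 50% | 22.27 − 21.47 = 0.80 | 25.07 − 20.80 = 4.27 |

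At q = 0.40 the largest value at 50% uptake is 23.22 − 15.82 = 7.40 months. If mF = mU the two curves coincide and the overstatement is zero.

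**4. What the choice of rule does.** At q = 0.20, d = 0, u = 0.50, over the mU and mF values above, median PFS in months is:

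| Rule | Median |
|---|---|
| New therapy as an event | 20.0–21.5 |
| Umbralisib only (not observable) | 20.8–23.5 |
| Censored at new therapy | 23.4–24.9 |
| As followed | 23.7–26.5 |

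Counting new therapy as an event falls below the umbralisib-only value and censoring falls above it, because non-responders are assumed to do worse than responders.

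**The case against.** The strongest reply is that following patients through later therapy is a legitimate treatment-policy approach, and that the definition and follow-up rules already work that way. That stands as far as it goes: PFS can be computed as written, and the fix keeps it as the main analysis. But the plan never declares the choice, and the result does not answer the objective in 2.1. Nor does the plan call for the start date of new therapy, without which no other rule can be applied reliably.

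It is also fair that ORR alone decides the trial, that 2.1 ranks PFS as secondary, and that uptake and frontline PFS are unknown. These limit the weight of the point. Section 9.9.1 gives no null value for the log-rank test, so the effect on that test cannot be assessed.

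A reader might infer more than the documents support:

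- *That the ORR type I error is inflated.* This would need responses after a switch to be counted, at a rate the documents do not give. No such intent is shown, and the stop rule speaks of response to umbralisib.
- *That the overstatement is likely to reach 7.4 months.* That figure belongs to the null ORR, where the trial stops at stage 1 with probability 0.82.
- *That progression at Cycle 3 will be rare because no CLL subject in the phase 1 study had it as best response.* Only 3 of those 20 were non-responders; 0 of 3 has an exact 95% upper limit of 1 − 0.025^(1/3) = 70.8%.
- *That the two PFS start dates differ by at most the screening window.* No section dates registration, so the gap cannot be bounded.
- *That outside therapy is nowhere addressed.* Section 4.4 does so for adverse events.

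**Conclusion.** The point holds, at the level of a change that should be made. PFS as defined is PFS of umbralisib followed by any subsequent therapy, and the plan presents it as PFS of umbralisib. That mismatch follows from the text alone. Its size does not: at the design ORR the illustration gives about 0.2 to 0.8, 0.4 to 2 and 0.8 to 4.3 months at 10%, 25% and 50% uptake. It rests on exponential times, a borrowed responder median and assumed medians for the other groups. The response cut-off is unwritten rather than misused, and the two-stage ORR design is otherwise correct. The conflicting PFS start dates and follow-up intervals are separate, smaller defects in the same analysis.

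**What to change.** 1. In 8.4 and 9.9.1, count only responses recorded before any non-protocol anti-CLL therapy towards best overall response and ORR, and start DOR only from such a response.
2. Record the start date of new anti-CLL therapy. Keep the as-followed PFS of 9.9.1 as the main analysis and label it there as PFS of umbralisib followed by subsequent therapy. Also report PFS with new therapy as an event and PFS censored at new therapy, with the number who switched. State that the first tends to understate and the second to overstate umbralisib PFS if non-responders do worse than responders.
3. Use one PFS start date in 2.2 and 9.9.1. Cycle 1 Day 1 is already in 9.9.1 and fits the treatment-based starting points in 8.4 and 9.1.
4. Reconcile 4.4, 6.5 and the schedule table on the progression follow-up interval and on assessment after Cycle 12. The interval is for the sponsor to set.

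Cost: wording changes, one CRF date field and two extra PFS analyses. Items 1 to 3 add no visits or scans. The downside is three PFS medians that will differ and need explaining.
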